5.3.3. Handling of Missing and/or Unquantifiable Immune Response Data

Missing immune response data will not be imputed.

Data below the LLOQ will be treated differently according to the statistical analysis.

- For the calculation of GMT, data below LLOQ will be imputed with $\frac{1}{2}$ of the LLOQ.
- For the calculation of geometric mean of fold change from prevaccination, data below LLOQ will be imputed with LLOQ.

Data above ULOQ will be imputed with the ULOQ.

The ULOQ and LLOQ values per assay will be available in the database.

5.4. Secondary Endpoint(s) Analysis

5.4.1. Non-inferiority Testing on MOPA

Analysis will be performed to evaluate the non-inferiority of MOPA functional antibody response against the vaccine O-serotype antigens after concomitant administration of ExPEC9V and a HD quadrivalent seasonal influenza vaccine versus the administration of ExPEC9V administered alone. The endpoint is given by:

- Opsonophagocytic antibody titers to vaccine O-serotype antigens as determined by MOPA at 29 days after the administration of ExPEC9V vaccine.

5.4.2. Antibody HI Titers

- Seroconversion is defined for each of the 4 influenza vaccine strains at 29 days after the administration of a HD quadrivalent seasonal influenza vaccine
 - HI titer $\geq 1:40$ in participant with a prevaccination HI titer of $< 1:10$, or
 - a ≥ 4 -fold HI titer increase in participant with a prevaccination HI titer of $\geq 1:10$
- Seroprotection is defined for each of the 4 influenza vaccine strains as HI titer $\geq 1:40$ at 29 days after the administration of a HD quadrivalent seasonal influenza vaccine

5.4.3. ExPEC9V O-serotype Antibody Titers

ExPEC9V serotype antibodies will be measured by multiplex ECL-based immunoassay and MOPA assays. The EPA is measured by multiplex ECL-based immunoassay only.

The immunogenicity endpoints are:

- Total serum immunoglobulin G antibody titers determined by multiplex ECL-based immunoassay
- Functional antibody titers determined by MOPA

The endpoints are evaluated between the two study vaccination groups at all immunogenicity time points, at Days 1, 30, and 59 for titers determined by multiplex ECL-based immunoassay and at Days 1 and 30 (relative to ExPEC9V vaccination, refer to Table 5) for titers determined by MOPA.

In addition, the two endpoints determined at 29 days after administration of ExPEC9V are evaluated between participants reporting a history and without history of UTI at enrolment.

5.4.4. Analysis Methods

As in the primary analysis, in all analyses that incorporate age group and history of UTI, the stratification factor data are obtained as collected from the eCRF. Supportive analyses for non-inferiority are performed by age group and history of UTI as stratified and recorded in IWRS.

A 2-sided 95% CIs for the difference in \log_{10} -transformed O-serotype opsonophagocytic antibody titers against each of the 9 O-serotypes at 29 days after the administration of ExPEC9V vaccine between the Control and the CoAd group will be evaluated to determine whether the immune response against O-serotype antigens after administration of ExPEC9V and a HD quadrivalent seasonal influenza vaccine is non-inferior compared to after the administration of ExPEC9V alone. As in the primary analysis method, an ANOVA model will be fitted with the respective titers as dependent variable and study intervention group, age group and history of UTI as independent variables. Based on these models, the CIs around the difference will be calculated and will be back transformed to CIs around a GMT ratio ($\text{GMT}_{\text{Control group}}/\text{GMT}_{\text{CoAd group}}$) and compared to the non-inferiority margin of 1.5.

As a sensitivity analysis to assess the impact of baseline titers, this secondary endpoint will also be evaluated adjusting for the respective baseline titers. For immunogenicity, baseline is considered as the last assessment prevaccination. In a second sensitivity analysis, different variances between the groups will be allowed. Therefore, the CIs will be calculated via Welch's ANOVA.

The proportion of seroconverted and seroprotected participants will be tabulated. The difference in proportions of seroconverted and seroprotected participants between the Control and the CoAd group will be estimated together with the 2-sided 95% CIs (calculated using Wilson's score method).

The following measures of ExPEC9V O-serotype antibody titers (ECL and MOPA) and the EPA (ECL) will be evaluated and tabulated at the immunogenicity timepoints by study vaccination groups stratified by age (≥ 65 to < 75 years, ≥ 75 years, and all) and by history of UTI. Analysis stratified by history of UTI in the combined study vaccination groups will also be performed.

- proportion of participants with a ≥ 2 -fold and ≥ 4 -fold increase in serum antibody titers from baseline (prevaccination)
- GMT
- geometric mean of fold change from baseline (GMR), calculated from the ratio of post baseline to baseline value (prevaccination)

Graphical representations of immunological parameters will be made as applicable.

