**9.1. Statistical Hypotheses**

For a description of the hypotheses, see Section [3](#)., Objectives and Endpoints.

The study is successful if both below objectives are demonstrated:

- non-inferiority of the humoral immune response to the 4 influenza vaccine strains after concomitant administration of ExPEC9V and a HD quadrivalent seasonal influenza vaccine versus the administration of a HD quadrivalent seasonal influenza vaccine administered alone,

*AND*

- non-inferiority of the humoral immune response against the O-serotype antigens after concomitant administration of ExPEC9V and a HD quadrivalent seasonal influenza vaccine versus the administration of ExPEC9V administered alone

Therefore, the following CIs will be calculated:

- the 2-sided 95% CIs for the difference in log10-transformed HI antibody titers against each of the 4 influenza vaccine strains at 29 days after the administration of the HD quadrivalent seasonal influenza vaccine between the Control and the CoAd group, and
- The 2-sided 95% CIs for the difference in log10-transformed O-serotype antibody titers against each of the 9 O-serotypes at 29 days after the administration of ExPEC9V between the Control and the CoAd group

Only if the upper bound of the 2-sided 95% CI for the GMT ratio (Control group/CoAd group) of the HI antibody titers for each of the 4 vaccine strains and of the O-serotype antibody titers for each of the 9 O-serotype antigens lies below 1.5, non-inferiority of co-administration versus separate administration will be concluded for both vaccines (seasonal influenza vaccine and ExPEC9V). If 1 or more confidence limits for the GMT ratio exceed 1.5, non-inferiority cannot be concluded.

As both non-inferiority objectives should be demonstrated to have a successful study, no multiplicity adjustment is needed.

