6.4. Appendix 4: Toxicity Grading Scale for Vital Signs.....	22
7. REFERENCES.....	23

VERSION HISTORY

Table 1: SAP Version History Summary

SAP Version	Approval Date	Change	Rationale
1.0	11 September 2023	Not Applicable	Initial release
2.0	21 May 2024	
(1) Added
 
 – MAAE to the safety analysis, – Non-inferiority testing based on MOPA functional titers at 29 days after the administration of ExPEC9V vaccine, – Description of the details and type of data to be reviewed by the IDMC. 
(2) Day 59 is removed from Table 6 (Visit Windows for HI Antibody Titers Immunogenicity Analysis).
 
(3) Data for the stratification factors, age and history of UTI will be obtained as collected from the eCRF; in addition, analysis using data from IWRS will be performed to support non-inferiority.
 
(4) Add ExPEC immunogenicity analysis stratified by baseline titer (titers \leq LLOQ and titers $>$ LLOQ).
 
(5) Minor changes (e.g., grammar, paragraph rearrangement) to the SAP for clarity.
	
(1) Requested by Health Authority.
 
(2) HI titer at Day 59 will not be available.
 
(3) Clarify the source of data for the stratification variables age and history of UTI, whether (as collected) from the eCRF or (as stratified) from IWRS.
 
(4) Interest in ExPEC immunogenicity analysis stratified by baseline immune status.

LIST OF ABBREVIATIONS

ADaM	Analysis Data Model
AE	adverse event
AS	All Screened
BMI	body mass index
CI	confidence interval
CoAd	Coadministration
CSP	clinical study protocol
E. coli	Escherichia coli
ECL	Electrochemiluminescent
eCRF	electronic case report form
EPA	exotoxin A derived from Pseudomonas aeruginosa
ExPEC9V	9-valent extraintestinal pathogenic Escherichia coli vaccine
FAS	full analysis set
GMR	geometric mean ratio
GMT	geometric mean titer
HD	high dose
HI	hemagglutination inhibition
IDMC	Independent Data Monitoring Committee
IWRS	interactive web response system
LLOQ	lower limit of quantification
MAAE	medically attended adverse event
MOPA	multiplex opsonophagocytic killing assay
PPEI	per protocol ExPEC immunogenicity
PPII	per protocol influenza immunogenicity
SAE	serious adverse event
SAP	Statistical Analysis Plan
ULOQ	upper limit of quantification
UTI	urinary tract infection

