5. STATISTICAL ANALYSES

5.1. General Considerations

The significance level (α) is 5% (2-sided). As both non-inferiority objectives should be demonstrated to have a successful study and as no interim analyses before the primary analysis are planned, no multiplicity adjustments are needed.

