5.3.2. Analysis Methods

The primary immunogenicity objectives will be assessed by calculating the following CI.

- The 2-sided 95% CIs for the difference in \log_{10} -transformed HI antibody titers against each of the 4 influenza vaccine strains at 29 days after the administration of the HD quadrivalent seasonal influenza vaccine between the Control and the CoAd groups.
- The 2-sided 95% CIs for the difference in \log_{10} -transformed O-serotype antibody titers against each of the 9 O-serotypes at 29 days after the administration of ExPEC9V vaccine between the Control and the CoAd group.

For HI antibody titers against each of the 4 influenza vaccine strains and for O-serotype antibody titers against each of the 9 O-serotypes, an analysis of variance (ANOVA) model will be fitted with the respective titers as dependent variable, and group (Control or CoAd), age category (≥ 65 to < 75 and ≥ 75 years) and history of UTI (yes/no) as independent variables. Based on these ANOVA models, the CIs around the difference will be calculated and will be back transformed (by exponentiation) to CIs around a GMT ratio ($\text{GMT}_{\text{Control group}}/\text{GMT}_{\text{CoAd group}}$) and compared to the non-inferiority margin of 1.5.

Only if the upper bound of the 2-sided 95% CI for the GMT ratio (Control group/CoAd group) of the HI antibody titers for each of the 4 vaccine strains and of the O-serotype antibody titers for each of the 9 O-serotype antigens lies below 1.5, non-inferiority of co-administration versus separate administration will be concluded for both vaccines (HD quadrivalent seasonal influenza vaccine and ExPEC9V). If 1 or more confidence limits for the GMT ratio exceed 1.5, non-inferiority cannot be concluded.

As a sensitivity analysis to assess the impact of baseline titers, the primary endpoint will also be evaluated adjusting for the respective baseline titers. For immunogenicity, baseline is considered as the last assessment prevaccination. In a second sensitivity analysis, different variances between the groups will be allowed. Therefore, the CIs will be calculated via Welch's ANOVA.

The primary analysis will be based on the stratification factors, age group and history of UTI reported in the database, as collected in the eCRF. Supportive analyses for non-inferiority will be performed by age group and history of UTI as stratified in IWRS.

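### SAP 2.0 adds a nine-serotype MOPA non-inferiority test without a success rule or a place after the primary, and its no-adjustment statement does not cover that test

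*SAP*

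**What the plan says.** **Where the MOPA test comes from.** Protocol Section 3 lists MOPA titers 29 days after ExPEC9V as a secondary endpoint used to evaluate immunogenicity further. Protocol 9.4.3 only tabulates them: fold-rise proportions, GMTs and geometric mean fold changes. The SAP version history for 2.0 (21 May 2024) adds "Non-inferiority testing based on MOPA functional titers at 29 days after the administration of ExPEC9V vaccine" and gives a Health Authority request as the reason.

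**What the SAP now does with it.** SAP 5.4.1: "Analysis will be performed to evaluate the non-inferiority of MOPA functional antibody response against the vaccine O-serotype antigens". SAP 5.4.4 fits the primary ANOVA model to each of nine serotypes, forms 2-sided 95% CIs for the Control/CoAd GMT ratio, compares them with 1.5, and says they are "evaluated to determine whether the immune response against O-serotype antigens after administration of ExPEC9V and a HD quadrivalent seasonal influenza vaccine is non-inferior".

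**The primary rule.** Protocol 9.1: "The study is successful if both below objectives are demonstrated", meaning influenza (4 HI strains) and ExPEC9V (9 O-serotypes). SAP 5.3.2 requires every one of these 13 upper bounds to lie below 1.5 and adds: "If 1 or more confidence limits for the GMT ratio exceed 1.5, non-inferiority cannot be concluded". SAP 5.3.1 fixes the assays for these endpoints as HI and ECL.

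**The multiplicity statement.** SAP 5.1 sets a 2-sided 5% level. It then notes that both primary objectives must be shown and, "as no interim analyses before the primary analysis are planned, no multiplicity adjustments are needed". Protocol 9.4.1, from September 2023, makes the same statement; the MOPA test was added later.

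**The concern.** The argument in SAP 5.1 is sound for the decision it describes. When a claim needs every comparison to pass, no adjustment is required. The MOPA test lies outside that argument in two respects.

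1. **No success rule.** SAP 5.4.4 takes over the model, CIs, margin and both sensitivity analyses from SAP 5.3.2, but not the paragraph saying that all comparisons must pass. The reference back to the primary method introduces the ANOVA model only.
2. **No ordering.** Nothing makes a MOPA conclusion depend on the primary. Nor is MOPA called descriptive, whereas SAP 5.6 says explicitly for safety that there will be no formal group comparisons.

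As written, a trial that misses one of the 13 primary comparisons could still report functional-antibody non-inferiority, for all nine serotypes or for some, at the nominal level. How many serotypes suffice would be settled by interpretation, possibly after unblinding. Since a Health Authority asked for the test, its decision rule should be fixed beforehand.

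**Working it through.** **Inputs.** From the documents: 2-sided α 5% (SAP 5.1); margin 1.5, SD 0.5 (HI) and 0.6 (ExPEC9V) on the log10 scale, 419 evaluable per group, true difference 0 (protocol 9.2); nine MOPA comparisons (SAP 5.4.4). Not in the documents, so assumed: the correlation ρ between test statistics (range 0 to 0.8) and the MOPA SD.

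**Step 1. Reproduce the plan's power and identify the per-test level.** The margin is log10(1.5) = 0.1761. The standard error is SD × √(2/419), which is 0.0345 for SD 0.5 and 0.0415 for SD 0.6. The noncentral t with 836 df at one-sided 2.5% gives:

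| | One comparison | All comparisons | Protocol 9.2 |
|---|---|---|---|
| HI, SD 0.5 | 99.91% | 99.65% (4th power) | 99.91%, 99.64% |
| ECL, SD 0.6 | 98.88% | 90.35% (9th power) | 98.88%, 90.36% |

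The stated figures reproduce to within rounding. One-sided 5% would give 99.97% and 99.53% for one comparison, so the plan works at one-sided 2.5% per test. That follows from the rule itself: the interval is 2-sided 95% and only its upper bound decides.

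**Step 2. Reading A: all nine serotypes must pass.** The MOPA claim is then an intersection-union test, so its error is at most 2.5%. There is no inflation within MOPA.

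Without a gate there are still two separate claims, primary and MOPA, each with error up to 2.5%. The worst case is one true ratio at the margin in each family and the rest far inside it. With ρ the correlation of those two limiting statistics, and P(both) the bivariate normal probability that both exceed 1.96:

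P(at least one false claim) = 0.025 + 0.025 − P(both)

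| ρ | P(both) | At least one false claim | Relative to 2.5% |
|---|---|---|---|
| 0 | 0.0006 | 4.9% | 2.0 |
| 0.5 | 0.0046 | 4.5% | 1.8 |
| 0.8 | 0.0110 | 3.9% | 1.6 |

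The bound whatever the correlation is 0.025 + 0.025 = 5%.

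**Step 3. Reading B: a single serotype may be claimed.** With all nine true ratios at 1.5, P(at least one false claim) is 1 − 0.975⁹ = 20.4% at ρ = 0. For equicorrelated statistics it is 1 − ∫φ(u) Φ((1.96 − √ρ·u)/√(1−ρ))⁹ du:

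| ρ | At least one false MOPA claim | Relative to 2.5% |
|---|---|---|
| 0 | 20.4% | 8.2 |
| 0.5 | 13.5% | 5.4 |
| 0.8 | 8.3% | 3.3 |

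**Step 4. With both rules stated.** If all nine must pass and MOPA is tested only after primary success, error is at most 2.5% across the two claims. If the primary null is true, any false claim needs a false primary success first (at most 2.5%). If it is not, only the MOPA claim can be false (at most 2.5%).

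**The case against.** **All nine is a natural reading.** SAP 5.4.4 asks one question about the response to the O-serotype antigens and treats MOPA as a single secondary endpoint. SAP Section 2 uses nearly the same phrase for the primary and spells it out as holding for each of the nine. This stands: the Reading B figures apply only if single-serotype claims are allowed, which the SAP neither permits nor rules out. It does not supply the missing gate.

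**The overall co-administration claim is protected.** A reader might infer that the trial's main conclusion carries an inflated error rate. The documents do not support that. Protocol 9.1 and SAP 5.3.2 allow that conclusion only when all 13 HI and ECL bounds are below 1.5, and MOPA is not part of study success.

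**The figures are worst cases.** They need true ratios exactly at the margin, and the correlations are assumed. Measured against the stated 2-sided 5% rather than the inferred one-sided 2.5%, the ungated all-nine case shows no excess. Both remarks are fair. The second turns on the reference level, and the plan's own power figures show that tests are run at 2.5% in the deciding direction.

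**Secondary endpoints often go uncontrolled.** That is acceptable when they are called supportive or descriptive. This one is not, and its wording is inferential. The documents do not show what use the Health Authority or the sponsor intends for the result, so a planned confirmatory claim cannot be assumed either.

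**The gate is partly a choice.** One failed influenza strain would block a conclusion on *E. coli* functional antibody. That is so, but a gate on the nine ECL comparisons alone would leave a false primary claim (through an HI strain) and a false MOPA claim able to add up as in Step 2.

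**Conclusion.** The gap is real and cheap to close. SAP 2.0 introduces a formal secondary non-inferiority test with no stated success rule and no position relative to the primary, and keeps a no-adjustment statement whose reasons do not extend to it. The primary conclusion and its type I error are unaffected.

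The size depends on a reading the SAP leaves open. If all nine serotypes are required, only the missing gate matters: up to 3.9% to 4.9% over the two claims, bounded by 5%, against 2.5%. If single serotypes may be claimed, the figure is 8.3% to 20.4% for at least one false MOPA claim. Both ranges run over assumed correlations of 0.8 to 0 at least favourable true ratios. It is tempting to give one inflation factor for the plan, but that would merge two different readings at a chosen correlation, and the documents give no correlation.

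**What to change.** **SAP 5.4.4 (with a pointer in 5.4.1).** State that MOPA non-inferiority is concluded only if the primary objective is met (all 13 comparisons) and the upper bound of the 2-sided 95% CI of the GMT ratio is below 1.5 for each of the nine serotypes. Otherwise the nine ratios and CIs are reported descriptively.

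**SAP 5.1.** State that the no-adjustment argument rests on the all-comparisons rule within each objective and on the fixed sequence from primary to MOPA.

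If no formal MOPA conclusion is wanted, labelling the comparisons descriptive in SAP 5.4.1 and 5.4.4 also closes the gap.

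**Cost.** Wording only. No CI, sample size or analysis changes, and every ratio and CI is still reported. The downside is that no confirmatory MOPA claim can be made in two situations:
- The primary fails: 1 − 0.9965 × 0.9035 ≈ 10% under the planning assumptions, with comparisons taken as independent.
- One MOPA serotype misses. The documents give no MOPA SD. With 419 per group, no true difference and independent comparisons, the chance that all nine pass is about 90% at SD 0.6, 65% at 0.7 and 35% at 0.8.

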**4. STUDY DESIGN****4.1. Overall Design**

This is a randomized, double-blind, placebo-controlled, parallel group, multicenter, Phase 3 study in adult participants aged 65 years and older.

A target of approximately 932 participants will be randomized in parallel in this study in a 1:1 ratio to 1 of 2 vaccination groups (Table 1). The randomization will be stratified by age category ( $\geq 65$  to  $< 75$  years,  $\geq 75$  years) and history of UTI (yes/no).

Group 1 (CoAd group) will receive ExPEC9V on Day 1 administered at the same time as HD quadrivalent seasonal influenza vaccine, and placebo on Day 30. Group 2 (Control group) will receive placebo on Day 1 administered at the same time as HD quadrivalent seasonal influenza vaccine, and ExPEC9V on Day 30. All study vaccinations will be given by the IM route.

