## 9.2. Sample Size Determination

Sample size calculations are performed under the following assumptions:

- No effect of co-administration of ExPEC9V and seasonal influenza vaccine on the immune response against influenza as measured by HI antibody titers against the 4 influenza vaccine strains at 29 days after the administration of influenza vaccine
- A standard deviation of 0.5 at the log10 scale for HI antibody titers against the 4 influenza vaccine strains at 29 days after the administration of influenza vaccine (with or without ExPEC9V)
- No effect of co-administration of ExPEC9V and seasonal influenza vaccine on the immune response against the O-serotype antigens as measured by antibody titers against the 9 O-serotype antigens at 29 days after the administration of ExPEC9V
- A standard deviation of 0.6 at the log10 scale for ExPEC9V antibody titers at 29 days after the administration of ExPEC9V (with or without seasonal influenza vaccine)
- A non-inferiority margin of 1.5
- 2-sided  $\alpha$  of 5%

---

 Non-inferiority criteria based on FDA guidance for influenza vaccines ([FDA 2007b](#)).

A total of 419 evaluable participants per group are needed to have 99.91% power to show non-inferiority in HI antibody titers for 1 influenza vaccine strain and to have 98.88% power to show non-inferiority in antibody titers against 1 O-serotype antigen. With this sample size, the overall power to show non-inferiority in HI antibody titers against each of the 4 influenza vaccine strains at 29 days after the administration of seasonal influenza vaccine as well as non-inferiority in antibody titers against each of the 9 O-serotype antigens at 29 days after the administration of ExPEC9V is at least 90% (see table below).

	1 comparison	All comparisons
Flu NI (SD=0.5)	99.91%	99.64% (4 comparisons)
ExPEC9V NI (SD=0.6)	98.88%	90.36% (9 comparisons)
Total		> 90% power

To account for 10% exclusions from the per protocol set (see below for definitions of analysis sets), drop-outs and missing samples, approximately 466 participants per group should be enrolled, resulting in a total sample size of approximately 932 participants.

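### The seroconversion and seroprotection differences leave out the randomisation strata; a stratified interval would be a small gain in precision at no cost

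*SAP*

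**What the plan says.** Protocol 4.1 states: "The randomization will be stratified by age category" and by history of UTI (yes/no). Protocol 6.3 repeats this, with permuted blocks and 1:1 allocation. SAP 5.3.2 puts group, age category and UTI history in the primary ANOVA, and SAP 5.4.4 does the same for the MOPA non-inferiority comparison.

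For the rate endpoints, SAP 5.4.4 and Protocol 9.4.3 agree with each other: "The difference in proportions of seroconverted and seroprotected participants between the Control and the CoAd group will be estimated", with 2-sided 95% CIs by Wilson's score method. Neither names a stratum or covariate. SAP 5.7.1 lists age and UTI history as immunogenicity subgroups, but that is not a stratified comparison of the groups.

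On the primary titers, SAP 5.3.2 adds: "In a second sensitivity analysis, different variances between the groups will be allowed", by way of Welch's ANOVA. SAP 5.4.4 repeats this for MOPA. Neither section says whether age category and UTI history stay in the model.

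**The concern.** When randomisation is balanced within strata, stratum differences in response add nothing to the true variance of the crude difference between groups. The crude variance formula still counts them. The interval is therefore too wide to the extent that the strata predict response. Eight secondary comparisons are involved (4 strains by 2 endpoints). They answer the first two secondary objectives on a different footing from the titer comparisons beside them.

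The Welch question is related. A sensitivity analysis is easiest to read when it changes one assumption. Standard Welch's ANOVA has a single factor, so, run as named, it would relax the equal-variance assumption and drop the covariates together.

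What is at stake is precision and ease of interpretation, not error control.

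**Working it through.** **1. The plan's own figures.** Inputs from Protocol 9.2 and SAP 5.1: "The significance level (α) is 5% (2-sided"); "A non-inferiority margin of 1.5", so log10(1.5) = 0.1761; "No effect of co-administration of ExPEC9V and seasonal influenza vaccine on the immune response against influenza", and likewise for the O-serotypes; "A standard deviation of 0.5 at the" log10 scale for HI; "A standard deviation of 0.6 at the" log10 scale for ExPEC9V; 419 evaluable per group. With SE = SD·√(2/419) and the noncentral t distribution:

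- HI: 99.91% for one strain; to the 4th power, 99.65% (stated 99.91% and 99.64%).
- ExPEC9V: 98.88% for one serotype; to the 9th power, 90.35% (stated 98.88% and 90.36%).
- All 13: 90.04% (stated as above 90%).
- Enrolment: 419/0.9 = 465.6, so 466.

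The plan's figures reproduce. It states no precision for the rate differences.

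**2. Rate differences.** For overall rate P and between-stratum variance of the rate V:

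- crude half-width = 1.96·√(2P(1−P)/n)
- stratified half-width = 1.96·√(2[P(1−P)−V]/n)
- ratio = √(P(1−P)/[P(1−P)−V])

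Assumptions, since the documents give none of these: 35% aged 75 or older, 30% with UTI history, additive effects a (age) and u (UTI). Then V = 0.35·0.65·a² + 0.30·0.70·u².

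| a / u (points) | Spread (points) | V | Excess width, P = 40-60% | P = 80% | P = 90% |
|---|---|---|---|---|---|
| 0 / 0 | 0 | 0 | 0% | 0% | 0% |
| 5 / 5 | 10 | 0.00109 | 0.2% | 0.3% | 0.6% |
| 10 / 10 | 20 | 0.00438 | 0.9% | 1.4% | not possible |
| 20 / 10 | 30 | 0.01120 | 2.3-2.4% | 3.7% | not possible |
| 20 / 20 | 40 | 0.01750 | 3.7-3.9% | not possible | not possible |

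(Not possible: a stratum rate would exceed 100%.)

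Example: P = 50%, 10 points each, n = 419. Crude 1.96·√(2·0.25/419) = 6.77 points; stratified 1.96·√(2·0.245625/419) = 6.71 points. The Newcombe interval built from Wilson limits gives 6.74 points for the crude case. The largest absolute loss in the table is about 0.24 points (6.77 against 6.53 at P = 50%, 20 points each).

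A second set of assumed shares gives the same picture: four evenly spaced strata weighted 42/28/18/12%. The variance of the stratum index (0 to 3) is 2.08 − 1.00² = 1.08, so V = 1.08·(spread/3)².

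- 12-point spread: V = 0.00173; excess width 0.3% at P = 50% and 0.5% at P = 80%.
- 25-point spread: V = 0.0075; excess width 1.5% and 2.4%.

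**3. Welch without covariates against the adjusted ANOVA.** HI titers, total SD 0.5, same 35%/30% shares, 2,000 simulated trials per case, strata balanced:

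| Age / UTI shift (log10) | Share of variance explained | Welch half-width ÷ ANOVA half-width | Welch coverage |
|---|---|---|---|
| 0 / 0 | 0% | 1.000 | 94.9% |
| 0.1 / 0.1 | 1.8% | 1.009 | 95.5% |
| 0.2 / 0.1 | 4.5% | 1.023 | 95.1% |
| 0.3 / 0.2 | 11.6% | 1.064 | 96.8% |

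For comparison, the effect of the variance assumption alone, with SDs 0.7 and 0.5:

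- 419 per group: pooled and Welch SE are both √((0.49+0.25)/419) = 0.04203.
- 400 (SD 0.7) and 440 (SD 0.5): pooled SE 0.0417, Welch SE √(0.49/400 + 0.25/440) = 0.0423.

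With near-equal groups, either change can move the interval by a percent or so. If both are made at once, the source of a difference cannot be read off.

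**The case against.** The strongest reply is that nothing depends on these intervals. Protocol 3 says only that the rates are to be compared, with no margin. Success rests on the 13 GMT-ratio intervals (Protocol 9.1, SAP 5.3.2). A crude risk difference is a legitimate descriptive summary, and the SAP follows the protocol. No document shows that age or UTI history predicts HI response: Protocol 2.1 links UTI history to baseline *E. coli* O-antigen responses, not to influenza. All of this stands, and it keeps the point minor. It does not argue for the crude interval, because a stratified one estimates the same quantity from data already collected.

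A reader might infer three stronger things that the documents do not support.

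- **That an unadjusted Welch analysis lowers joint nine-serotype power below plan, to 89.3%-83.8%.** That follows only if 0.6 is a residual SD after adjustment and the strata explain 2-10% of variance. Protocol 9.2 gives 0.6 as the SD of the titers and names no adjustment. On that reading the unadjusted analysis keeps 90.35%, and the adjusted model would gain (91.3%, 92.7% and 94.7% if the strata explain 2%, 5% and 10%).
- **That Welch's ANOVA cannot answer its question, because its SE equals the pooled SE at 1:1.** Equality needs equal evaluable numbers, not equal randomisation. For the ExPEC9V comparison, Control participants must also reach the second vaccination and the Day 59 sample, so numbers may differ. Agreement under balance is itself a robustness result, and the replacement proposed here would also match the pooled SE under exact balance.
- **That Wilson's method is wrong for a difference.** Applied to two proportions, it is naturally read as Newcombe's hybrid of Wilson limits. Naming that form would be a clarification.

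**Conclusion.** The point holds as a minor one. The rate differences are specified without the factors that govern randomisation and enter the neighbouring models. The resulting intervals are valid and err on the conservative side. The excess width is about 0-4% for assumed rates of 40-90% and assumed spreads of 0 to 40 points, and 0.3-2.4% for spreads of 12-25 points. It is zero if neither factor predicts HI response. Rates, stratum shares and stratum effects are all assumptions. The sample size, the success rule and the study conclusion are unaffected.

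The Welch part is a gap in specification, not an error. That the covariates would be dropped is an inference from the method's usual definition. If they are, half-widths grow by about 0-6% over the assumed effects, and the analysis changes two things at once.

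**What to change.** In SAP 5.4.4, estimate each seroconversion and seroprotection difference with Mantel-Haenszel weights over the four cells of age category by UTI history. Give a stratified Newcombe (Wilson-based) or Miettinen-Nurminen 95% CI. Take the factors from the eCRF, as that section already does for other analyses. If the crude difference is intended, say so and name the two-sample form of the interval.

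In SAP 5.3.2 and 5.4.4, define the unequal-variance analysis as the primary model (group, age category, UTI history) with group-specific residual variances and Satterthwaite degrees of freedom, so that only the variance assumption changes.

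The cost is a few lines of SAP text and standard code. Protocol 9.4.3 has the same wording, so the SAP should record the change as a refinement of it. No new data are needed, and the decision rule stays as it is.
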